3.3 Study design

Study type:	Two-armed randomized controlled clinical study	
Study arms:	2	
Study centers:	Paracelsus Medical University, Institute of Ecomedicine	
	Department of Internal Medicine I	
	with Gastroenterology - Hepatology, Nephrology, Metabolism and Diabetology University Hospital Salzburg	
Sponsor:	Investigator sponsored and initiated trial / Funding: Horizon Europe RESONATE, Project Nr. 101081420	
Control group:	Yes (Waiting-List Control Design)	
Randomization:	Yes	
Allocation ratio:	1:1	
Observation period:	180 days	
Analysis:	Intention-to-treat	

4 Methods: Study participants, Intervention and Outcome Parameters

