4.3 Intervention

Nature-based therapy (NBT) consists of the components green exercise/hiking and nature-based mindfulness training.

The hikes are designed to accommodate individuals with varying levels of fitness. Each hike lasts between 1.5 and 2 hours. Participants will traverse distances between 3 and 6 kilometers and ascend to elevations of up to 300 meters on the Salzburg city mountains. A heart rate monitor (wristwatch) will be provided to each participant, which will be calibrated to their specific gender, age, height, and weight. This monitor will be used throughout the intervention. It is recommended that participants complete the hikes within the range of 60-70% of their maximum heart rate (Steele et al., 2021). Additionally, it is advised that training be conducted at a medium level of exertion on the Borg scale (12-16) (Borg, 1982; Löllgen, 2004). A guided group is limited to a maximum of 15 participants and is accompanied by a hiking guide and a mindfulness trainer.

Mindfulness training is based on concentrative movement therapy (Stolze & Badura-MacLean, 2002), a body psychotherapy method that combines physical movements and concentration to promote awareness and mindfulness of one's own body. The objectives of this form of mindfulness training are threefold: firstly, to enhance body awareness through targeted movement exercises; secondly, to reduce stress and promote general well-being; and thirdly, to cultivate mindfulness by training individuals to focus their attention on the present moment.

Intervention group (Nature group) :

Week 1 (day 0 - day 7): Onboarding

- a. 3 x 1,5-2h Green Exercise (guided hikes on the Salzburg city mountains,
 3-6 km each, 100-300 hm, max. 15 people per group)
- b. Within these hikes, participants will receive 20 minutes of nature-based mindfulness training under the guidance of a therapist in a pre-selected restorative and safe location. It is important to note that participants will learn mindfulness training during the process so that they can continue to practice it independently.
- c. It is required that all participants engage in the guided hikes during the initial week of the program.

Week 2 – Week 5 (day 8 – day 35): Integration

- a. 3 x 1,5-2h Green Exercise per week (guided or self-guided hikes (participants can choose) on the Salzburg city mountains, 3-6 km each, 100-300 hm)

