4.5 Study timeline

Participation in the clinical study involves four measurement time points over a period of 180 days:

- **T1 (day 1):** Baseline data assessment directly before the intervention for intervention and control group; data assessment at the premises of the Paracelsus Medical University Salzburg
- **T2 (day 35):** data assessment after the onboarding (week 1) and integration phase (week 2-5) for all study participants of the intervention and control group at the premises of the Paracelsus Medical University Salzburg
- **T3 (day 70):** data assessment for all study participants of the intervention and control group after the first follow-up phase (week 6-10) at the premises of the Paracelsus Medical University Salzburg
- **T4 (Tag 180):** data assessment for all study participants of the intervention and control group after the first follow-up phase (week 6-10) via online questionnaire

[figure not shown]

Figure 1: Study timeline

The present clinical study is planned in two rounds:

- Round 1: from September 2024: intervention group, waiting list control group
- Round 2: ab March 2025: intervention group, waiting list control group

The implementation in two rounds results from the capacities of the study team (hiking guides, therapists).

For ethical reasons, the control group is designed according to the principle of a waiting list control group (Elliott & Brown, 2002). This implies that the individuals in the control group will also have the chance to benefit from the nature-based therapy. The offer will be made to the control group after all measurements have been completed (after t4) in spring and fall 2025.

The allocation of groups is random.

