5.1 Randomization

Randomization is carried out using an open source add-in for Microsoft Excel (Kraus, 2014). Age and gender are to be used as stratification factors. The Kullback-Leibler divergence method is to be used as the allocation method (Endo et al., 2006). Randomization and stratification are performed by a biometrician who is not involved in the recruitment of study participants. The necessary stratification factors are blinded to the staff performing the group allocation.

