6.3 Statistics

All statistical analyses will be performed using the R-GNU software environment (General Public License, R Foundation for Statistical Computing, Vienna, Austria) and SPSS (IBM). Statistical significance will be set at the level of a < 0.05 for all tests. Randomly missing values will be replaced using the standard procedure, last outcome carried forward (LOCF). The statistical analysis will be carried out by a biometrician. The data will be blinded again in order to exclude a possible bias with regard to an expected result.

Statistical analyses will be performed in accordance with the intention-to-treat principles and reporting will adhere to the CONSORT-statement, including CONSORT flow chart (Calvert et al., 2013; CONSORT, 2019).

After a positive vote, the study will be preregistered in the ISRCTN registry (https://www.isrctn.com/).

Check for normal distribution

The Shapiro-Wilk test will be applied to check for normal-distribution. Depending on data distribution, parametric or non-parametric tests will be applied.

Analysis of Baseline values

To analyze possible baseline differences between the two groups, a t-test for unconnected samples is performed for normally distributed variables and a Mann-Whitney Utest for non-normally distributed parameters. Nominally scaled variables are analyzed using the chi-square test. If any baseline variables are significantly different between the groups, secondary analysis will be conducted including these variables to adjust for any residual confounding not prevented by the randomization.

Longitudinal Data analysis

Depending on data distribution, parametric or non-parametric tests will be applied. Participant data will be compared in terms of baseline data, including outcome variables as well as demographics (unpaired Student-T-Test or Wilcoxon-test).

For longitudinal data analysis, analyses of variance (ANOVA) or linear mixed models (LMM) are used for normally distributed data.

For non-normally distributed samples, a non-parametric analysis of variance (e.g. f1.LD.f1) is performed using the nparLD package (Noguchi et al., 2012).

Models will include random effects for temporal and spatial correlations and fixed effects for: (1) intervention group; (2) time effects characterizing changes between pre- and post-intervention; and (3) interaction between the intervention group and the pre- and

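### The longitudinal models use the baseline outcome only as a time point and omit age and gender; the sole covariate adjustment, a secondary one, is chosen by baseline significance tests

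*Protocol*

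**What the plan says.** **Allocation.** Protocol section 5.1 states "Age and gender are to be used as stratification factors" and "The Kullback-Leibler divergence method is to be used as the allocation method". The design therefore deliberately balances these two variables.

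**Model terms.** Section 6.3, under longitudinal data analysis, states "Models will include random effects for temporal and spatial correlations and fixed effects for: (1) intervention group". It then adds time and the group-by-time interaction. The interaction is named as the group contrast that decides whether the intervention works. The baseline visit is one of the time points. No covariate is listed. Non-normal outcomes go to a non-parametric analysis such as f1.LD.f1.

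**Adjustment.** Section 6.3 tests the arms against each other at baseline with t, Mann-Whitney or chi-square tests. The comparison covers outcome variables as well as demographics. It then says, in two places, "If any baseline variables are significantly different between the groups, secondary analysis will be conducted including these variables". The significance level is common to everything: "Statistical significance will be set at the level of a < 0.05 for all tests".

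**The concern.** Three features of the stated plan sit badly together.

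1. The baseline outcome is usually the strongest predictor of the follow-up outcome. Used only as a time point with a free mean in each arm, it is subtracted in full, however weakly it correlates with follow-up. Used as a covariate, it is weighted by that correlation. The second use is never less precise in large samples, and the data are already collected.
2. Variables that steer the allocation should normally be in the analysis, so that the standard errors reflect the balance the design imposes. Here they are not.
3. A significance test between randomised arms asks whether chance produced the difference, and under valid randomisation the answer is known. The test ignores how prognostic a variable is. It can pick up an irrelevant variable and pass over a strong predictor with a moderate imbalance. Age and gender, being balanced by design, are the variables least likely to be picked. Because outcomes are among the variables tested, the rule could also add baseline SF-12 as a covariate to a model that already holds baseline SF-12 as a response.

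At stake are precision that costs no new data, and an adjusted analysis whose content cannot be known before the data are seen. The protocol fixes both the model terms and the selection rule itself, so this is not a detail left to a later document.

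**Working it through.** **Inputs from the protocol**
- 70 per arm and 40% assumed loss to day 180 (sections 4.6 and 4.7); "Allocation ratio: 1:1" (section 3.3).
- Simulated power of 0.817 at n=40 and 0.873 at n=50 per arm (section 4.6, Table 1).
- Level 0.05; sidedness is not stated and two-sided is assumed here.

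**Assumed inputs (not in the protocol)**
- Pre/post correlation r, shown from 0.5 to 0.8.
- Number of baseline tests k, shown at 20 and 30.
- R², the share of the variance of the analysed contrast explained by age and gender.

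**The plan's own figure.** 70 × 0.6 = 42 completers per arm, and 42/0.6 = 70. Table 1 has no row for 42. Linear interpolation gives 0.817 + 0.2 × (0.873 − 0.817) = 0.828. A normal approximation anchored at n=40 implies a standardised effect of (1.96 + 0.904) × √(2/40) = 0.640. It gives 0.835 at n=42, and 0.893, 0.939 and 0.966 at 50, 60 and 70, against 0.873, 0.942 and 0.962 in Table 1. The approximation is close enough for illustration. The point does not depend on how 70 was reached.

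**Step 1: baseline outcome as covariate.** For one pre and one post measure with equal variances and complete data, per participant:
- change score: 2σ²(1 − r)
- covariate-adjusted: σ²(1 − r²)
- ratio: (1 − r²)/(2(1 − r)) = (1 + r)/2

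| r (assumed) | Variance ratio | Equivalent extra participants, 2/(1+r) − 1 | Illustrative power at 42 per arm (change score 0.835) |
|---|---|---|---|
| 0.5 | 0.75 | 33% | 0.92 |
| 0.6 | 0.80 | 25% | 0.91 |
| 0.7 | 0.85 | 18% | 0.89 |
| 0.8 | 0.90 | 11% | 0.87 |

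The power column treats the Table 1 effect as if it applied to a change-score contrast.

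**Step 2: age and gender.** With complete data, a covariate that does not vary over time cancels from a within-person difference. A random-intercept model fitted to simulated data (84 participants, three visits) confirms this: the standard error of the group-by-time term was 0.1951 with and without age and sex as main effects. In simulated trials with balanced allocation, where age and sex predicted the level but not the change, power for the change contrast was the same with and without them (0.71 and 0.71). Where they also explained 10% or 20% of the change, adding them raised power from 0.67 to 0.71 and from 0.63 to 0.69.

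Omitting balanced factors that do predict the contrast makes the test conservative. The actual level is 2(1 − Φ(1.96/√(1 − R²))): 0.048, 0.044, 0.039 and 0.028 for R² of 0.02, 0.05, 0.10 and 0.20.

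**Step 3: chance selection.** For k independent tests, the probability of at least one significant difference is 1 − 0.95^k:
- k=20: 1 − 0.358 = 0.64
- k=30: 1 − 0.215 = 0.79

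If the variables share a common correlation of 0.3, these fall to 0.54 and 0.66; at 0.5 they fall to 0.42 and 0.51. The range of k is plausible given the allostatic load components, questionnaires, spirometry and blood analysis in section 4.4, but the protocol gives no count.

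**The case against.** The strongest reply is that section 6.3 calls the triggered adjustment a secondary analysis. That stands. A reader might infer that the main result adjusts for whatever differs by chance, but the text does not say so: the listed models adjust for no covariate, and chance selection cannot move their estimate.

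A second reply is that leaving out age and gender has not been shown to cost precision. That also stands for the contrast the protocol defines. A reader might infer an inflated error rate or a clear loss of power from the omission; Step 2 shows no change in the ordinary complete-data case and, if anything, a conservative test. The gain in Step 1 comes from the baseline outcome, at values of r that the protocol does not give.

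A third reply is that f1.LD.f1, as specified with one group factor and time, has no place for covariates, although it is one of the two analysis paths and the basis of the sample size. This is correct, and it shapes the fix.

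A reader might go further and object that round and hiking group are missing from the model. The protocol does say "The implementation in two rounds results from the capacities of the study team (hiking guides, therapists" and "A guided group is limited to a maximum of 15 participants", but the stronger conclusion does not follow. Both arms run in each round, so round does not bias the comparison, and adding it is a preference. Guided hikes are compulsory only in week 1, optional in weeks 2 to 5 and not offered in weeks 6 to 10. The protocol does not say that groups are fixed, lists no group identifier, and gives no intraclass correlation. Any figure for clustering would rest on assumptions alone.

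**Conclusion.** The point holds in limited form. The stated models make poor use of the baseline outcome and leave out the two allocation factors, and the only adjustment rule selects covariates by tests that, under randomisation, detect nothing but chance.

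The size is moderate and conditional. The variance of a single pre/post contrast would be 15 to 25% lower for an assumed r of 0.7 to 0.5, with complete data. The secondary adjusted analysis has a 64 to 79% chance of being triggered for an assumed 20 to 30 independent tests, and less with correlated ones. For age and gender the argument is agreement between analysis and allocation; precision improves only if they predict change. Nothing here invalidates the main comparison. It is a low-cost improvement that should be made before the data are analysed.

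**What to change.** In section 6.3:

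- Name, for the primary outcomes, a linear mixed model of the post-baseline visits with group, visit and group-by-visit, plus the baseline value of that outcome, age and gender as covariates. An equivalent choice is a model that constrains the baseline means to be equal across arms; age and gender must then have terms that can act on the post-baseline means, since main effects alone add essentially nothing.
- Keep f1.LD.f1 as an unadjusted sensitivity analysis.
- Delete the baseline significance tests and both statements of the adjustment they trigger. Describe baseline data by arm without p-values.

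**Cost.** The change is to wording and uses variables already collected. The real downside is that the mixed model, not f1.LD.f1, becomes primary for non-normal outcomes. The primary method then no longer depends on a normality test, but it differs from the method used to simulate the sample size, and the protocol should say so.

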3.2 Research questions

A two-arm randomized controlled clinical trial (NATURE-MET-S) is to be conducted based on the initial situation described above.

The primary objective of the clinical study is to analyze the impact of a multimodal nature-based therapy combining green exercise and mindfulness training on biopsychological resilience in a sedentary population with metabolic syndrome and low nature contact prior to the study.

Primary outcomes to measure biopsychosocial resilience are:

1) Quality of Life and 2) Allostatic Load,

The secondary objective is to provide data on environmental, social, and economical aspects of the intervention to contribute to innovation actions and to establish nature-based therapies as secondary prevention measure in health care.

In addition to the NATURE-MET-S study, similar studies on nature-based secondary prevention of MetS are being conducted simultaneously in Padua (Nature-Met-P) and Barcelona (NATURE-MET-B) to compare different types of nature exposure. The three studies are jointly developed and implemented. Although these are not multicenter studies, they are three comparable nature-based intervention studies for people with MetS (Barcelona, Salzburg) or at risk of MetS (Padua). This allows for a comparison of the effects of different types of natural environments: 1) coastal blue in Barcelona, 2) urban green in Padua, and 3) rural mountainous in Salzburg

The following research questions are to be investigated in the NATURE-MET-S study:

- 1) What is the effect of a nature-based intervention on biopsychosocial resilience in patients with Metabolic Syndrome compared to a control group (T1 day 1, T2 day 35, T3 day 70)?
 - a. Does health-related quality of life improve? Primary Outcome
 - b. Does the Allostatic Load Index improve? Primary Outcome
 - c. Are there changes in vital and lung function parameters and in the complete blood count? *Secondary Outcome*
 - d. Are there any changes in psychological and health economic parameters? *Secondary Outcome*
- 2) How sustainable are possible effects of the nature-based intervention compared to the control group? (T1 day 1 -T4 day 180)?
 - a. Are there sustainable changes in psychological and health economic parameters up to day 180 (online questionnaire)? *Secondary Outcome*
- 3) How is the nature-based intervention evaluated by the study participants? (T1 day 1 -T4 day 180)?
 - a. individual sessions Primary Outcome

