4.4.2 Secondary endpoints

The analysis of the following parameters is defined as secondary endpoints

III. Secondary endpoints t1-t3

- 1) Vital parameter and lung function parameters
 - a. height, weight, oxygen saturation
 - b. forced expiratory spirometry (PEF, FEV1, FVC, MEF)
- 2) Laboratory parameters
 - a. full blood analysis (blood sampling from the vein) 4

IV. Secondary endpoints t1-t4

- 1) Resilience (questionnaires)
 - a. State-Trait-Assessment of Resilience Scale (STARS), (Lock et al., 2020), German version

⁴ A total of 25 ml of blood is taken.

- b. Perceived Stress Scale, German version (Cohen et al., 1983; Schneider et al., 2020)
- c. Brief Sense of coherence scale (SOC-3) (Schumann et al., 2003)
- 2) Mindfulness (questionnaires)
 - a. Five Facet Mindfulness Questionnaire (FFMQ-15) (Baer et al., 2012), German version
- 3) Physical activity (Questionnaire)
 - a. International Physical Activity Questionnaire Short Form (IPAQ-SF), German version (IPAQ, 2019)
- 4) Nature contact (questionnaires)
 - Nature connectedness (Inclusion of Nature in Self Scale (INS), German version, (C. Martin & Czellar, 2016; adapted from P. W. Schultz, 2002) and Nature Connectedness Index (NCI)
 - b. Direct nature contact (People and Nature Survey 2023, M1-Q1, (Marshall, 2023)
 - c. Indirect nature contact (Gu et al., 2023; adapted from L. Martin et al., 2020)
- 5) Subjective well-being and quality of life (questionnaires)
 - a. Intercultural Quality of Life Comic (Pichler, 2020)
 - b. OECD-4 (OECD, 2013)
- 6) Social aspects (questionnaires)
 - a. Loneliness: German short version of the De Jong Gierveld Loneliness Scale (Gierveld & Tilburg, 2006)
 - b. Community cohesion: German short version of the Community Cohesion Scale, (Weinstein et al., 2015)
- 7) Motivation (questionnaires)
 - a. Ideal self, based on (Ganesan, 2020)
 - b. Self-determined motivation (Astell-Burt et al., 2024)

V. Integrative evaluation parameters (t1-t4)

- 1) Environmental aspects (t1-t4):
 - a. (Perception of local nature, PANS-6, People & Nature Survey 2023 (Marshall, 2023))
 - b. Environmental concerns adapted from (W. Schultz, 2001)
 - c. Pro-Environmental Behavior, Revised Pro-Environmental Behavior Scale (R-PEBS), adapted in consultation with the author (Brick et al., 2017)
- 2) Health economic aspects (t1-t4)
 - a. Quality Adjusted Life Years (QUALY): calculation from SF-12

- b. Use of Care Services (cost savings)

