6.2 Data management

The REDCap database is used for digital data collection. Each study participant will be assigned a six-digit identification number (ID) for anonymization purposes. Personal data will only be stored in ID-encrypted form. The password-protected master list, which contains the assignment of IDs to personal data, ensures that personal data can be deleted when the study is completed. The master list is stored on a secure data server at the Paracelsus Medical University of Salzburg and is only accessible to the researcher responsible for recruitment, eligibility checks and allocation. Data from medical examinations and surveys are stored in spreadsheet files. Only authorized researchers have access to the data. Participants can access their personal data after completion of the study.

Written consent will be obtained from all study participants for the use of their personal data. The consent forms will include a specific clause on the protection of personal data, informing study participants of how their data will be handled and stored, the purpose of the research, the contact details of the data protection officer and their rights.

All personal data will be handled as defined in General Data Protection Regulation (EU 2016/679), and Finnish Data Protection Act 1050/2018.

Each person involved in the conduct of the study (hiking guides, assistants, etc.) will sign a confidentiality agreement before the start of the study, which will be countersigned by the principal investigator of the study. Confidentiality refers to all circumstances that become known through participation in the study, in particular information about study participants, employees and other cooperation partners regarding economic, operational, technical, tax and personal circumstances as well as internal matters of any kind.

The data will be used for scientific purposes and for possible publication in scientific journals and conferences. In addition, the results of the study will be used for the further development and implementation of effective, sustainable and cost-effective nature-based therapies (including health equity, nature conservation and health economics aspects).

Saliva samples from the Padua (NATURE-MET-P) and Barcelona (NATURE-MET-B) studies will be sent to the Paracelsus Medical University for analysis. The probes will only be labelled with an identification number (ID), so the analysis will be completely anonymous and experimenter-blinded.

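### Section 6.3 exempts no outcome from its distribution rule, so skewed care use, which the protocol ties to cost savings, would be judged by a rank test that does not estimate a mean saving

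*Protocol*

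**What the plan says.** Section 6.3 sets one route for choosing the analysis. "The Shapiro-Wilk test will be applied to check for normal-distribution", and then: "Depending on data distribution, parametric or non-parametric tests will be applied". Under longitudinal data analysis, normally distributed data go to ANOVA or linear mixed models. For the rest, the protocol says: "For non-normally distributed samples, a non-parametric analysis of variance (e.g. f1.LD.f1) is performed using the nparLD package". The group-by-time interaction is the contrast that decides whether the intervention works. Section 6.3 does not single out any outcome for different treatment.

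The health economic items fall within the outcomes to be analysed:

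- Section 3.2 states: "The secondary objective is to provide data on environmental, social, and economical aspects of the intervention". Question 1d asks: "Are there any changes in psychological and health economic parameters". It is labelled a secondary outcome, and question 2a extends it to day 180.
- Section 4.4.2, group V, lists "Quality Adjusted Life Years (QUALY): calculation from SF-12" and "Use of Care Services (cost savings)", both at t1-t4.

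The protocol describes no separate analysis for these items: no mean cost difference, bootstrap, generalised linear model or cost-effectiveness ratio. It gives no unit costs, recall window or expected distribution.

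**The concern.** Total cost is the mean per person times the number of people. A saving is therefore a difference in arithmetic means, whatever the shape of the data. The non-parametric branch asks which arm tends to have the higher value. Under it, a hospital stay fifty times as costly as a clinic visit moves the result only by its place in the ordering.

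If the arms differ only in location, this matters little for the sign. If one arm has more low-level use but fewer very costly episodes, or the reverse, the two summaries can part. A significant rank result could then be read as evidence for or against a saving when the means show something else. This would remain even if the model for the SF-12 and the Allostatic Load Index were settled, because only the economic items need the arithmetic mean for their interpretation.

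**Working it through.** The plan has no figure of its own to reproduce here. All cost figures below are assumptions.

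**Inputs from the protocol.** 70 per arm (4.6, 4.7); 40% loss by day 180 (4.6), so 70 × (1 − 0.40) = 42 completers per arm; significance level 0.05 (6.3), sidedness not stated and taken as two-sided.

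**1. Would the rule send care use to ranks?** For assumed negative-binomial counts (mean 2, k = 0.7; mean 4, k = 1.5), Shapiro-Wilk rejected normality in 100% of simulated samples at N = 84 and N = 140. With skew of that order the rank branch follows.

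**2. Can ranks and means disagree? Three-point example.**

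| Cost | Control | Intervention |
|---|---|---|
| 0 | 0.70 | 0.55 |
| 100 | 0.25 | 0.44 |
| 5000 | 0.05 | 0.01 |

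- Control mean: 0.25 × 100 + 0.05 × 5000 = 25 + 250 = 275.
- Intervention mean: 0.44 × 100 + 0.01 × 5000 = 44 + 50 = 94.
- Mean saving with the intervention: 275 − 94 = 181 per person.
- P(intervention > control) = 0.44 × 0.70 + 0.01 × 0.95 = 0.3175.
- P(equal) = 0.55 × 0.70 + 0.44 × 0.25 + 0.01 × 0.05 = 0.4955.
- Relative effect = 0.3175 + 0.5 × 0.4955 = 0.565. Above 0.5 means a tendency to higher use in the intervention arm.

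**3. The reverse direction.** Let all 70 controls cost 300. Let 63 intervention participants cost 200 and 7 cost 1500. The intervention mean is (63 × 200 + 7 × 1500)/70 = 330, which is 10% higher, but 63/70 = 90% of the intervention arm lies below every control. Ranks point to a saving that the means do not show.

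**4. How often would it be significant?** In the three-point example with 42 per arm, a Mann-Whitney test at a single time point was significant in 24% of simulated trials. That is not the contrast in 6.3. An approximate group-by-time contrast on overall midranks, with both arms on the control distribution at baseline, was significant in at most about 19% (within-person correlation 0.5) and less often at correlation 0.

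A second assumed case uses lognormal costs with a mean of 1000 in both arms and log-SDs of 1.0 (control) and 1.5 (intervention), so the true mean saving is zero. The approximate group-by-time rank contrast was significant in 57% of trials with 42 per arm and 79% with 70 per arm.

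**5. When do they agree?** If intervention costs are control costs plus a constant, the mean difference is that constant, and the relative effect lies on the same side of 0.5. The sign then agrees.

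**The case against.** Several objections have force.

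- **Coverage is inferred.** Section 6.3 never mentions care use, costs or QALYs, and a statistical analysis plan or health economic plan, not shown, may treat them separately. This stands as a caution. The point, however, is the stated rule: it has no exemption, the protocol refers to no other cost analysis, and the listed endpoints are its own. That f1.LD.f1 is given only as an example changes the routine, not the choice of a non-parametric method.
- **QALYs.** A reader might infer that nparLD would be run on QALYs and could reverse their sign. A QALY total is one value per person, so f1.LD.f1 does not fit it, and no reversal has been shown. The general sentence on parametric or non-parametric tests would still reach a non-normal QALY total.
- **Cost-effectiveness as an endpoint.** Section 6.2 speaks of "effective, sustainable and cost-effective nature-based therapies". A reader might take this as a promised cost-effectiveness result. It describes how results will be used and is not an endpoint.
- **Question 1d asks only about changes.** A rank test on care use can answer that. It cannot quantify the saving named beside the item in 4.4.2.
- **Certainty.** A reader might conclude that the rank branch is certain, or that care use is mostly zero. The protocol gives no data for either. Some recruitment is through metabolic, diabetes and obesity clinics, where zero use may be uncommon.
- **Reporting.** Nothing in 6.3 forbids mean costs beside the test, so it would be too strong to say the question cannot be answered.

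**Conclusion.** The point holds in limited form. Applied as written, 6.3 judges skewed care use, and any costs derived from it, by a rank test whose target is not the mean difference that a saving requires. The two can differ in sign: means of 275 and 94 in favour of the intervention against a relative effect of 0.565 the other way.

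That size rests wholly on an assumed distribution, chosen to combine more low-level use with fewer very costly cases. A disagreement in the actual trial is possible and is not predicted. The simulated rates depend equally on assumed shapes, and any multiplicity adjustment under 6.3 would lower the number of significant results. The endpoints concerned are secondary. Conclusions on the SF-12 and the Allostatic Load Index do not change.

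**What to change.** Add one statement to 6.3, or a pointer to the economic analysis plan if one exists:

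- Care use, and any costs derived from it, are exempt from the Shapiro-Wilk rule.
- They are summarised by the between-arm difference in arithmetic means per randomised participant, adjusted for baseline, with a bootstrap 95% confidence interval. A log-link generalised linear model that accommodates zeros is an alternative.
- The QALY total is handled the same way for consistency.

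nparLD can remain for ordinal questionnaire outcomes. The change needs no extra participants or data collection, and the bootstrap is routine in R. The price is wide intervals for mean costs at 42 to 70 per arm. They should be reported as they are, because they show how little the trial can say about savings.
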